#### **4.4 Subject Withdrawal Criteria**

All subjects are free to withdraw from participation in this study at any time, for any reason, specified or unspecified without prejudice to subsequent care. Withdrawn dosed subjects will not be replaced. A subject may be withdrawn from the study under any of the following circumstances:

- Withdrawal of informed consent
- If, in the opinion of the investigator, Institutional Review Board/Independent Ethics Committee/Research Ethics Board (IRB/IEC/REB), Health Authority and/or Shire, it is no longer in the subject's best interest to continue in the study
- Subject no longer meets all inclusion criteria or meets any criterion for exclusion
- Lack of compliance with study procedures or study drug administration, as determined by the investigator
- Occurrence of an SAE determined by the investigator to be possibly related to study drug and not alleviated with treatment of symptoms
- Adverse event
- Hypersensitivity determined by the investigator to be possibly related to study drug
- Pregnancy or lactation
- Administrative reasons
- Treatment with commercial drug (Natpara)

In all cases, the reason for withdrawal must be recorded in the subject's medical records. If the reason is not known, the subject must be followed up to establish whether the reason was an AE and, if so, this must be reported in accordance with the procedures described in Section [6.2.1](#).

As far as possible, all examinations scheduled for the end-of-study evaluations must be performed on all subjects who participate but do not complete the study according to protocol.

## 5 TREATMENTS AND TREATMENT PLAN

### 5.1 Treatments Administered

Subjects will self-administer an SC injection of rhPTH[1-84] at a starting dose of either 25 or 50 µg daily into alternating thighs, based on their total serum calcium level at baseline as described in Section 3.1.

#### 5.1.1 Identification of Investigational Product(s)

RhPTH[1-84] is manufactured using a strain of *E. coli* modified by DNA technology and is identical to native human PTH. rhPTH[1-84] is a single-chain polypeptide containing 84 amino acid residues. The drug substance is clear and colorless to light straw-colored.

rhPTH[1-84] parathyroid hormone (rhPTH) product is provided in a dual-chamber cartridge. The front chamber (chamber 1) contains a sterile, white to off-white lyophilized powder containing rhPTH[1-84], sodium chloride, mannitol and citric acid. The rear chamber (chamber 2) contains a sterile diluent for reconstitution (m-cresol and sterile water for injection).

This study was initiated with study drug being administered using the Ypsomed pen injection device, in which the dual-chamber cartridge is installed by the user into a reusable pen injector device, in which reconstitution occurs in a total volume of 1.15 mL.

Based on the preliminary results of a recent study (PAR-C10-005) comparing the Haselmeier pen to the Ypsomed pen, showing that the two pens are bioequivalent; the Haselmeier pen has now replaced the Ypsomed pen in this study. The date the injection pen is switched will be recorded for each study subject.

In the case of the Haselmeier pen, the dual chamber cartridge comes pre-inserted in a cartridge holder. The cartridge in the cartridge holder is reconstituted using the Duoject mixing device and then loaded into the Haselmeier pen. The reconstituted volume is also 1.15 mL. Instructions for Use (IFU) for the Haselmeier pen and mixing device are provided in [Appendix 1](#).

Both pen injectors serve as holders for the cartridge and do not come in contact with rhPTH product. Using either pen injection device, each dual-chamber cartridge is designed to deliver 14 doses of 71.4 µL, each dose containing either 25, 50, 75, or 100 µg of rhPTH. The pen and reconstituted rhPTH product should be stored under refrigeration.

#### 5.1.2 Packaging and Labeling

##### Packaging

The study drug will be packaged, labeled, and delivered to the clinical centers by the sponsor or designee. Each subject will receive two pens for use during the study period and sufficient cartridges to provide daily doses for the duration of the study. Drug cartridges will be provided

in kits containing eight cartridges each and each kit will be sufficient for up to 16 weeks of treatment. Each cartridge will contain study drug for 14 doses. Drug cartridges will be provided at each clinic visit in sufficient quantity and at appropriate dose levels to ensure uninterrupted administration until the next study visit. Ancillary supplies including single use needles (31-gauge) and alcohol wipes will also be provided; once the inventory of ancillary kits is depleted, the clinical centers will receive the ancillary kit components separately and not as a kit (injection pen needles and alcohol prep pads).

### **Labeling**

Study drug will be supplied in individual kits labeled with the following information: investigational drug warning, company name, protocol number, lot number, storage conditions, contents, instructions regarding general dosing, and brief SC administration instructions. Label space will be provided for recording center and subject numbers. The label on the kit will be a tear-off label, which the study center can affix to the subject's source document or study document provided for this purpose. Boxes containing pens will be labeled with the following info: investigational warning, company name, protocol number, lot number, and subject number.

#### **5.1.3 Storage, Accountability, and Stability**

The clinical center's pharmacist or delegate is responsible for ensuring that all study drug received at the center is inventoried and accounted for throughout the study. All study drug must be kept in a locked area with access restricted to specific study personnel. The study drug and supplements are to be stored according to the manufacturers' specifications. The investigator or designee (ie, pharmacist) will conduct an inventory upon receipt of the clinical supplies from the sponsor, and will acknowledge receipt of the supplies to the sponsor or designee. A copy of the shipping documents must be maintained for the investigator's records.

Prior to reconstitution, cartridges should be stored at 2°C to 8°C (36°F to 46°F). After study drug reconstitution, the device can be used for up to 14 days when stored refrigerated at 2°C to 8°C and with infrequent exposure to room temperature for up to 30 minutes per day. Cartridges must be replaced 14 days after reconstitution. Cartridges should not be exposed to temperature extremes and should not be used if they have been or currently are frozen. Additional instructions for the storage of the Haselmeier pen and Duoject mixing device are included in the IFU.

In this study, subjects will be supplied with cartridges in sufficient quantity to maintain daily self-administration of varying dose of rhPTH[1-84]. Subjects should be reminded to return all cartridges, even if empty, at each study visit.

Pharmacy records will be maintained to capture the following information by lot number for each drug:

- quantity received
- current quantity on site
- quantity administered to each subject

- quantity removed from stock but not dispensed (eg, damaged, dropped, spilled)
- quantity remaining at the end of the study and retained, returned as per the sponsor's instructions

For each subject, dates that study medication was dispensed, administered, returned, or otherwise disposed of will be recorded.

All original containers, whether empty or containing study drug will be returned to the pharmacy. Contents of the study drug containers will not be combined. Unused study drug will be returned according to the sponsor's instructions.

## **5.2 Methods of Assigning Subjects to Treatment Groups**

Subjects will utilize the same 8-digit subject number that they had been assigned during the REPLACE or RELAY study. The first 4 digits consist of the center number and the last 4 digits are the sequential subject number. Subjects will receive study treatment in an open-label fashion at starting doses of rhPTH[1-84] 25 or 50 µg SC QD, as described in Section 3.1. On Day 1, the kit number from which cartridges are dispensed to a subject will be recorded on the appropriate eCRF. All subsequent kit numbers will be similarly recorded. All doses of study medication for each subject must be taken from the kit(s) designated for that subject and cartridges from an assigned kit will not be dispensed to any other subject.

## **5.3 Dose Regimens**

Daily rhPTH[1-84] SC injections will be self-administered into alternating thighs each morning using a multidose pen injection device (see [Appendix 1](#), Instructions for Use for the Haselmeier Pen Injector System).

### **5.3.1 Selection of Doses in Study**

rhPTH[1-84] given as a daily SC injection of 100 µg was approved in 2006 in the European Union for the treatment of postmenopausal osteoporosis (PMO). There is an extensive safety database with this product in subjects with PMO at doses ranging between 0.02 to 5.0 µg/kg. The phase 2 and 3 studies alone exposed 2891 subjects with PMO to doses ranging between 50 to 100 µg of rhPTH[1-84].

In subjects with hypoparathyroidism, several phase 1/2, single-center, open-label studies have demonstrated preliminary biologic activity of rhPTH[1-84] and PTH(1-34) given as daily or alternate day SC injections ([Bilezikian 2008](#); [Winer et al. 1998](#); [Winer et al. 2003](#); [Winer et al. 2008](#)). This current study will utilize varying doses starting at either 25 or 50 µg SC QD with the potential for upward adjustments in increments of 25 µg to a maximum dose of 100 µg SC QD, in order to assess its long-term effect in hypoparathyroid subjects.

### **5.3.2 Selection and Timing of Dose for Each Subject**

Subjects will self-administer rhPTH[1-84] in the morning, using the multidose pen injector devices. On the days of clinic visits, the injections of study drug will occur after the serum is taken for laboratory assessments and may be administered by the clinic study personnel.

Calcium and/or vitamin D should be taken in the morning as normal after the rhPTH[1-84] injection.

### 5.3.3 Compliance with Dosing Regimens

Paper diaries will be provided for the subjects to record study drug administration and supplement regimens. Subjects should be requested to bring the diaries to each clinic study visit for review. Subjects with  $\geq 80\%$  to  $\leq 120\%$  compliance level will be considered to be compliant with regard to study drug administration. Diaries will be collected at monitoring visits and submitted to the sponsor.

## 5.4 Prior and Concomitant Medications

### 5.4.1 Exclusionary Prior/Concomitant Medications

Subjects may remain on baseline concomitant medications during the trial (eg, hormone replacement therapy, antihypertensives, calcium-sparing diuretics, etc.). Prohibited prior and concomitant medications are generally those that may affect bone metabolism, confound efficacy or safety measurements, potentially pose a safety concern, or adversely potentiate or antagonize study drug therapy. Incidental or transient use of most of these medications (see list below) will not preclude a subject's entry into this study.

Exclusionary concomitant medications are shown in [Table 5-1](#).

**Table 5-1 Prohibited Medications or Therapies**

Medication/Therapy
Raloxifene hydrochloride
Bisphosphonates, intravenous
Bisphosphonates, oral
Calcitonin, cinacalcet or other drugs that influence calcium or bone metabolism
Fluoride tablets

Over the counter medications such as TUMS® are not to be taken as calcium supplementation. Please refer to Section [5.4.2](#) for information on calcium and vitamin D supplementation.

Permissible medications are:

- Nonprescription topical medications (that are not systemically absorbed)
- Acetaminophen
- Oral, implantable, vaginal rings, transdermal patch and injectable contraceptives and/or hormone replacement therapy
- All prescription and over the counter medication (including vitamins, herbs, or dietary supplements) being taken at baseline and all medications started during the study (from

signing the ICF through study exit), including administration dates and dosage, are to be recorded in the source document. Any medication which contains either calcium or vitamin D must be recorded in the source document with the amount of calcium and/or vitamin D content. To the extent possible, no changes should be made to the concomitant treatment during the study. Any additions, deletions or changes in the dose of these medications during the study also will be recorded in the source document.

#### **5.4.2 Active Vitamin D, Calcium, Native Vitamin D, and Magnesium Supplementation**

##### **Active Vitamin D**

Subjects enrolled in this study will be taking active vitamin D to control serum calcium levels. Oral calcitriol supplements will be provided during the first 52 weeks of this study by the sponsor or designee; no other sources of calcitriol should be used during the first year of study. Prescribed doses of calcitriol will be recorded in the source document. Calcitriol will not be supplied for the long-term extension portion of this study.

##### **Calcium**

Oral calcium supplements (either calcium carbonate or calcium citrate) will be provided throughout this study through approximately May 2014. Calcium citrate will continue to be supplied through the long-term extension; calcium carbonate will not be supplied through the remaining long-term extension portion of this study. No other sources of calcium supplementation should be used during the study. Calcium supplements should be taken regularly with meals, ideally morning and evening. Prescribed doses of calcium will be recorded in the source document.

In the case that extra calcium supplementation is taken by the subject due to symptoms of hypocalcemia, the dose/time and associated symptoms should be recorded by the subject in the diary.

##### **Native Vitamin D [25(OH) vitamin D]**

The serum 25(OH) vitamin D levels will be measured at the beginning of the study and at all scheduled study visits through the End of Treatment visit. During the study, sufficient supplemental native vitamin D should be administered in order to maintain the subject's serum 25(OH) vitamin D level in the normal range. Any dose taken by the subject must be recorded in the source document.

##### **Magnesium**

Magnesium is required for normal parathyroid function and disordered magnesium levels can exacerbate hypoparathyroidism. Subjects with low serum magnesium should undergo supplementation at a clinically appropriate level until the serum magnesium is within the normal range and normal serum magnesium should be maintained throughout the remainder of the study. Any dose taken by the subject must be recorded in the source document.

## **6 STUDY EVALUATIONS AND PROCEDURES**

### **6.1 Efficacy Evaluations**

Efficacy variables will be assessed by one or more of the following evaluations:

- Laboratory test results
  - Total serum calcium
  - 24-hour urinary calcium excretion
  - Serum phosphate
- Supplement usage
  - Concomitant supplemental oral calcium dosage
  - Concomitant supplemental oral calcitriol dosage

### **6.2 Safety Evaluations**

Safety variables will be assessed by the following evaluations:

- Adverse events and serious adverse events
- Incidence of AEs of hypocalcemia (eg, paresthesia, numbness, tetany) and hypercalcemia (eg, constipation, nausea, poor appetite or vomiting, frequent urination, thirst, and kidney stones)
- Incidence of hypercalciuria
- Immunogenicity analysis (AEs and SAEs related to PTH antibodies)
- Laboratory test results
  - Hematology (hematocrit, hemoglobin, white blood cells, red blood cells, platelets, differential)
  - Serum chemistries (standard Chem-20 panel, including calcium, phosphate, and albumin)
  - Serum 25-hydroxyvitamin D levels
  - Serum 1,25-dihydroxyvitamin D levels
  - Creatinine clearance
  - Serum bone turnover markers
  - Urinalysis
  - 24-hour urine calcium, phosphate, sodium, and creatinine excretion
  - PTH and ECP antibodies (Any subject who tests positive for PTH-specific antibodies at the last 2 consecutive visits at which antibodies are measured and does NOT continue treatment on commercial Natpara, will have follow-up blood draws for PTH antibodies at Months 3 and 6 poststudy. If a subject's results are negative at Month 3, follow-up may be terminated. Subjects may remain on study if they develop

PTH-specific antibodies during the study, providing that there are no concurrent AEs related to immunogenicity.)

- Bone mineral density by DXA
- Electrocardiogram parameters
- Physical examinations (including vital signs)
- Reason for termination from the study
- Pen-related events and/or complaints

### **6.2.1 Adverse Events**

The investigator is responsible for the detection and documentation of any AE or SAE, as defined in this protocol, during the study. Adverse events that were ongoing at the end of the REPLACE or RELAY study will be recorded and updated for this study. Any newly occurring AEs in this study will be recorded separately.

#### **6.2.1.1 Adverse Event Definition**

An AE is defined as any untoward medical occurrence in a subject or clinical investigation subject administered a pharmaceutical/medicinal product. An AE does not necessarily have to have a causal relationship with this treatment.

An AE can therefore be any unfavorable and unintended sign (including a clinically significant abnormal laboratory finding, for example), symptom, or disease temporally associated with the use of a medicinal product (investigational or marketed), whether or not considered related to treatment with the medicinal product.

An AE includes:

- An exacerbation of a pre-existing illness, sign, symptom, or clinically significant (as determined by the investigator) laboratory test abnormality and clinically significant ECG abnormality
- An illness, sign, symptom, or clinically significant laboratory abnormality that is detected or diagnosed after study drug administration
- Pretreatment or post-treatment events that occur as a result of protocol-mandated procedures

An AE does not include:

- The disease or disorder being studied or signs and symptoms associated with the disease or disorder, unless there is worsening of the condition of the disease or disorder
- A pre-existing disease or condition, present at the start of the study, that does not worsen

#### **6.2.1.2 Abuse, Misuse, Overdose, and Medication Error**

Abuse, misuse, overdose, or medication error (as defined below) must be reported to the sponsor according to the SAE reporting procedure whether or not they result in an AE/SAE as described

in Section 6.2.2.2. Note: The 24-hour reporting requirement for SAEs does not apply to reports of abuse, misuse, overdose, or medication errors unless these result in an SAE.

The categories below are not mutually exclusive; the event can meet more than 1 category.

- Abuse – Persistent or sporadic intentional intake of investigational product when used for a non-medical purpose (eg, to alter one's state of consciousness or get high) in a manner that may be detrimental to the individual and/or society
- Misuse – Intentional use of investigational product other than as directed or indicated at any dose (Note: this includes a situation where the investigational product is not used as directed at the dose prescribed by the protocol)
- Overdose – Intentional or unintentional intake of a dose of an investigational product exceeding the prescribed daily dose of the product
- Medication Error – An error made in prescribing, dispensing, administration, and/or use of an investigational product. For studies, medication errors are reportable to the sponsor only as defined below.

Medication errors should be collected/reported for NPSP558 (rhPTH[1-84]) only. Cases of missed doses are not considered reportable as medication errors. The administration and/or use of an expired investigational product should be considered as a reportable medication error.

#### **6.2.1.3 Procedures for Reporting Adverse Events**

Adverse events may be spontaneously reported by the subject, obtained through nonleading questioning, or noted during examination of a subject. All AEs and SAEs will be recorded from the signing of the ICF through the last study visit or the last study required procedure (including the follow-up telephone call 4 weeks after end of treatment). SAEs will be monitored with a telephone call by the investigator, as necessary, for approximately 4 weeks after the last dose of study drug, or until resolution or the SAE is judged by the investigator to have stabilized.

The AE term should note the diagnosis whenever possible, not the individual signs or symptoms (eg, myocardial infarction should be recorded rather than chest pain, elevated cardiac enzymes, and abnormal ECG). Also recorded are:

- Start and stop date and time
- Whether the event is continuing
- Frequency (intermittent, continuous)
- Intensity (mild, moderate, severe)
  - Mild: usually transient, requiring no special treatment and generally not interfering with usual daily activities
  - Moderate: usually ameliorated by simple therapeutic maneuvers and impairs usual activities
  - Severe: requires vigorous therapeutic intervention and interrupts usual activities. Hospitalization may or may not be required.

- Relationship to study drug (not related, related): identify relationship as “related” if a causal relationship between the investigational product and an AE is at least a reasonable possibility (ie, the relationship cannot be ruled out)
- Whether the AE is serious (ie, an SAE). If identified as an SAE, the AE should be reported on the SAE form according to Section 6.2.2.2 below.
- Actions taken (none; study drug dose changed, interrupted, or discontinued; other medication change; nondrug therapy)
- Outcome (resolved, resolved with sequelae, ongoing, fatal). An individual AE receives only one outcome.

Adverse events that are related to study drug and that have not resolved at the end of treatment will be followed by the site until resolution or until the AE is judged by the investigator to have stabilized.

Laboratory values, blood pressure, ECG evaluations, and clinical findings at the scheduled physical examinations must be reported as AEs if they:

- Are considered clinically significant by the investigator
- Fulfill SAE criteria, and/or
- Cause subject discontinuation from the study.

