- Adjustment of supplemental calcium and calcitriol regimens will be based on serum calcium levels, with the goal to be a reduction or removal of calcitriol treatment to the maximum degree clinically possible and to decrease the prescribed oral calcium supplementation to  $\leq 500$  mg daily.
- Subjects will have blood draws to assess total serum calcium levels (which may be performed locally) 3 to 5 days after ANY dose adjustment of rhPTH[1-84], after any significant change in doses of calcium and/or and calcitriol supplements, or at any other time

at the discretion of the investigator. Results of local total serum calcium levels will be recorded in the source document.

[figure not shown]
- Once a subject achieves a stable serum calcium (target: between 8.0 and 9.0 mg/dL) with the minimum doses of supplements possible, they will be maintained at that dose of rhPTH[1-84].
- If ANY predose (trough) total serum calcium is > 11.9 mg/dL study drug will be stopped. Once total serum calcium returns to the normal range, rhPTH[1-84] can be reintroduced. The rhPTH[1-84] dose may be maintained at the previous level if reductions in oral calcium supplements and/or calcitriol are possible. If oral calcium supplements have been previously reduced to ≤ 500 mg daily and calcitriol has been eliminated, then rhPTH[1-84] should be reintroduced at the next lowest dose level and supplemental oral calcium and calcitriol should then be adjusted accordingly to obtain a predose total serum calcium level of approximately 8.0 to 9.0 mg/dL.
- If the predose total serum calcium level remains above 10.0 mg/dL for two or more safety assessments or study visits on normal dietary intake and study drug alone, then the rhPTH[1-84] dose may be reduced to the next lowest dose level and supplemental oral calcium and calcitriol then adjusted accordingly to obtain a predose total serum calcium level of approximately 8.0 to 9.0 mg/dL. Study medication will be stopped if the predose total serum calcium remains above the upper limit of the laboratory normal range (ULN) for two or more safety assessments or study visits (no more than 5 days apart) at the lowest dose regimen, following withdrawal of all supplementary oral calcium and calcitriol therapy. Further choices on adaptation of treatment regimens, reinstitution of previous therapy, or discontinuation from study will be made in consultation with the Shire medical monitor.

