### Significant Hypercalcemia

Any instances of significant hypercalcemia, which is defined as any total serum calcium level of > 11.9 mg/dL (even on a non-trough measurement), require **MANDATORY** immediate stopping of rhPTH[1-84] treatment. Suspension of dosing with calcitriol and oral calcium as clinically appropriate and testing of serum total calcium levels at least daily should be undertaken until the subject's serum total calcium returns to the normal range. Other clinically appropriate actions for the treatment of significant hypercalcemia should be undertaken as usual by the investigator to ensure subject safety. Thereafter, rhPTH[1-84] can be reintroduced with clinically appropriate doses of calcitriol and oral calcium, with the aim to avoid further episodes of abnormal serum calcium.

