6.8.2. Clinical Laboratory Evaluation

All laboratory parameters will be collected and processed via a central laboratory, with exception of all urine pregnancy tests and total serum calcium levels which will be done at investigator's local laboratories. Standard international (SI) units will be used for data presentation. Only scheduled lab parameters will be included in the lab summaries. All lab data will be included in the listings.

Quantitative results will be summarized for hematology, serum chemistry, thyroid function tests (levothyroxine and thyroid-stimulating hormone), creatinine clearance, urinary chemistries (24-hour urine calcium, phosphate, and sodium excretion), and selected urinalysis parameters (pH, specific gravity, and urobilinogen) by visit. Both actual values and change from baseline will be summarized. Additionally, shift tables will be presented, summarizing cross tabulations of low,

normal, and high based on the parameter normal range, from baseline to each post-baseline visit and EOT. Percentages for shift tables will be based on the number of subjects with both baseline and post-baseline values at each visit.

Categorical urinalysis findings and urine pregnancy results will be presented in appendix data listings only.

Estimated creatinine clearance rate will be re-calculated based on the Cockcroft-Gault (C-G) equation:

$$\text{CLcr (mL/min)} = [140 - \text{age (years)}] \times \text{weight (kg)} \{ \times 0.85 \text{ for female subjects} \} / (72 \times \text{serum creatinine (mg/dL)}),$$

Estimated creatinine clearance rate will be summarized by stages as defined in Table 5.

Table 6.1 Definition of the Stages of Clcr3

Stage	Description	CLcr (mL/min)
1	Control (normal) Glomerular filtration rate (GFR)	≥ 90
2	Mild decrease in GFR	60-89
3	Moderate decrease in GFR	30-59
4	Severe decrease in GFR	15-29
5	End Stage Renal Disease (ESRD)	<15 not on dialysis
		Requiring dialysis

The number and percentage of subjects with post-baseline results qualifying as markedly abnormal will be summarized by parameter. A listing of all values for the parameter which qualifies as markedly abnormal will be provided. Markedly abnormal laboratory criteria are defined in Table 6.

Table 6.2 Markedly Abnormal Laboratory Criteria⁴

Lab parameter	Unit	Lower Limit	Upper Limit
Chemistry			
Albumin	g/L	≤20	≥90
Alkaline Phosphatase	U/L	NA	>2*ULN
ALT	U/L	NA	>3*ULN
Amylase	U/L	≤15	≥350
AST	U/L	NA	>3*ULN
Bilirubin	μmol/L	NA	>2*ULN
BUN	mmol/L	NA	≥10.7

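### The plan never says whether a calcium value that forces a study-drug stop (> 11.9 mg/dL) is an AE, so an asymptomatic stop and restart found on an interim draw can be missing from every incidence summary

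*Protocol*

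**What the plan says.** **AE rule.** Protocol 6.2.1.3 states: "Laboratory values, blood pressure, ECG evaluations, and clinical findings at the scheduled physical examinations must be reported as AEs if they" satisfy any of three conditions. The first is judgement: "Are considered clinically significant by the investigator". The second is meeting SAE criteria. The third is "Cause subject discontinuation from the study". Sections 6.2.1.1 and 6.2.3 repeat the judgement test. Interruption of drug appears in 6.2.1.3 only as an action recorded for an event that is already an AE.

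**Stop rule.** Appendix 2 makes the stop mandatory: "Any instances of significant hypercalcemia, which is defined as any total serum calcium level of > 11.9 mg/dL (even on a non-trough measurement". Section 3.1 ties the same threshold to predose (trough) values, and then says: "Once total serum calcium returns to the normal range, rhPTH[1-84] can be reintroduced".

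**Endpoint.** Protocol 6.2 lists "Incidence of AEs of hypocalcemia (eg, paresthesia, numbness, tetany) and hypercalcemia". The examples given for hypercalcemia are symptoms and kidney stones, not calcium values. Laboratory results are a separate safety endpoint.

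**Visit instructions.** Section 6.4.1 names episodes of hypercalcemia among the AEs to record, and 6.4.3 to 6.4.6 include any incidences of it in the AE evaluation. None gives a calcium cut-off.

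**SAP.** Section 6.8.1 identifies hypercalcemia by 'clinical preview', which is not defined, and counts subjects and episodes over the trial. On laboratory data, 6.8.2 says: "Only scheduled lab parameters will be included in the lab summaries". All laboratory data go into listings. Table 6.2 flags total calcium as markedly abnormal from 3.0 mmol/L.

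**The concern.** The stop above 11.9 mg/dL does not depend on judgement, but whether the value is reported as an AE largely does. Serum calcium must be checked 3 to 5 days after any change in rhPTH[1-84] dose or any significant change in supplements. These checks fall between clinic visits and may be done locally, so interim draws are a likely place to find a high value.

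The primary objective is to demonstrate long-term safety, and Appendix 2 names hypercalcemia as something to be avoided while supplements are reduced. If some sites record an asymptomatic stop-threshold value as an AE and others do not, the reported incidence is biased downward and partly reflects site habit.

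**Working it through.** The plan gives no hypercalcemia rate, power or sample-size basis to reproduce. The check follows one event through each planned output and then compares the two calcium thresholds.

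**Step 1. Follow the event.** Take an asymptomatic subject with calcium above 11.9 mg/dL on an unscheduled interim draw, whose drug is stopped and then restarted.

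- *AE rule (Protocol 6.2.1.3).* The SAE test is not met unless the event qualifies on other grounds. The discontinuation test is not met because the subject stays in the study. Only the judgement test remains.
- *Visit instructions (Protocol 6.4.1, 6.4.3 to 6.4.6).* They point toward recording but give no cut-off. The matching row in Tables 6-1 to 6-3 refers to clinical episodes, and in Table 6-1 it is not marked at the Week 1 interim calcium check.
- *Hypercalcemia counts (SAP 6.8.1).* Inclusion depends on what 'clinical preview' means. Prevalence is assessed on visit dates, which an interim draw can miss.
- *AE categories (SAP 6.8.1).* Discontinuation and death have categories; drug interruption has none.
- *Exposure (SAP 6.6.1).* Days on treatment and days dosed are summarized. Mandated stops are not counted.
- *Laboratory summaries (SAP 6.8.2).* An unscheduled value is excluded and appears in a listing only.

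No planned summary is certain to count this subject.

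**Step 2. Compare the thresholds.** Calcium has an atomic mass of 40.078 (assumed; not in the documents), so mmol/L = mg/dL × 10 / 40.078.

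- Stop threshold: 11.9 × 10 / 40.078 = 2.969 mmol/L
- One step above: 12.0 × 10 / 40.078 = 2.994 mmol/L
- SAP limit converted back: 3.0 × 40.078 / 10 = 12.02 mg/dL

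A value of 12.0 mg/dL meets the stop rule but is below the SAP flag. If results are reported to one decimal (an assumption), 12.0 is the only value in the gap.

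**Step 3. Size.** With N of about 50, one uncounted subject changes incidence by 1/50 = 2 percentage points. As an illustration only, 3/50 = 6% (exact 95% CI 1.3% to 16.5%). If none of the three is called an AE, the result is 0/50 = 0% (0% to 7.1%).

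**The case against.** The strongest reply is that the plan already leans toward recording these events. Appendix 2 labels any value above 11.9 mg/dL as significant hypercalcemia and requires at least daily retesting. Against that label, an investigator could hardly call the value not clinically significant. The visit instructions add hypercalcemia to the AE evaluation, and SAP 6.8.1 does not limit its counts to the three tests in 6.2.1.3. This stands to the extent that a reader who infers that such an event is counted only if each site chooses to call it an AE goes too far. It does not close the gap, because none of these provisions names a cut-off or refers to the stop.

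A reader might also infer that the values are lost. The documents do not support that. Scheduled high values reach the low/normal/high shift tables, and all laboratory data are listed. Section 3.1 says "Results of local total serum calcium levels will be recorded in the source document", but the summary of changes explains that this wording replaced references to the CRF because CRF instructions sit in other manuals, and Section 7.1 requires study data to be entered in the eCRF. Whether local calcium values reach the database cannot be settled from these documents.

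Finally, the threshold gap is narrow and the study is descriptive, with no formal testing. Both points are correct. They limit the consequence to under-counting in a descriptive safety summary; no test result is at risk.

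**Conclusion.** The point holds as a gap between sections. The AE rule, the visit instructions, the Appendix 2 definition and the SAP method for identifying hypercalcemia are not tied together, and the laboratory summaries do not fully cover for them. Complete absence from incidence summaries is confined to unscheduled draws, and it requires that the investigator does not report the value and that 'clinical preview' does not pick it up.

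The size is 2 percentage points per uncounted subject at about 50 subjects. The number of such events is unknown, so the total bias cannot be estimated; its direction is downward. The threshold mismatch (11.9 against about 12.02 mg/dL) is a minor contributor; the exclusion of unscheduled draws matters more.

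The trigger itself is also inconsistent: Section 3.1 refers to predose values, while Appendix 2 includes non-trough values. These passages must be reconciled before stop-threshold events can be counted without ambiguity. No view is taken on which is right.

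**What to change.** **Protocol.** In 6.2.1.3, add that a laboratory value triggering a protocol-mandated stop of study drug is reported as an AE with action taken 'interrupted', whether the sample was central or local. Align 6.2.3, the visit instructions in 6.4, and Appendix 2 with this. Reconcile the predose wording in 3.1 with the non-trough wording in Appendix 2.

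The trigger should not extend to values that lead only to dose reduction or titration. Section 3.1 allows downward adjustment to keep calcium at about 8.0 to 9.0 mg/dL, while Section 1.1 gives a normal range of generally 8.4 to 10.2 mg/dL. A wider trigger would therefore turn routine titration at normal calcium values into hypercalcemia AEs.

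**SAP.** In 6.8.1, replace 'clinical preview' with a stated definition of hypercalcemia events. Tabulate the number and percentage of subjects, and the number of episodes, with calcium above the protocol's stop threshold, using all recorded values including local and unscheduled ones.

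**Cost.** A few sentences in each document, a site reminder, a little extra site reporting, and one additional table. The reported hypercalcemia rate may be slightly higher. No treatment rule changes.
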